## 8. MEASUREMENT OF EFFECT

### 8.1 Definitions

**Evaluable for toxicity:** All participants who receive at least one dose of study treatment will be evaluable for toxicity from the time of their first treatment.

**Evaluable for objective response:** Only those participants who have measurable disease present at baseline, have received at least one cycle of therapy, and have had their disease re-evaluated will be considered evaluable for response. These participants will have their response classified according to the definitions stated below. (Note: Participants who exhibit objective disease progression or die prior to the end of cycle 1 will also be considered evaluable.)

### 8.2 AL Amyloidosis Hematologic Response Criteria

CATEGORY	RESPONSE CRITERIA
Complete response (CR)	
 
Normal serum free light chain ratio
 
Negative serum and urine immunofixation electrophoresis
 

Very good partial response (VGPR)	
 
Difference in serum free light chains less than 40 mg/L
 

Partial Response (PR)	
 
>50% Reduction in the difference in serum free light chains
 

Stable Disease (SD)	
 
Meets neither criteria for CR, VGPR, PR or PD
 

Progressive Disease (PD)	
 
From CR, an increase in serum M-protein to > 0.5 g/dL, an increase in the urine M-protein to > 200 mg/day, or an increase in the serum monoclonal free light chain by > 10 mg/dL (100 mg/L). From VGPR, PR or SD, an increase in the serum M-protein from the lowest level by > 50%, as long as the absolute magnitude of this increase is > 0.5 g/dL; or an increase in the urine M-protein from the lowest level by 50%, as long as the absolute magnitude of this increase is > 200 mg/day; or an increase in the serum or urine monoclonal free light chain by > 50% from the lowest level, as long as the absolute magnitude is > 10 mg/dL (100 mg/L).
 

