### 1.1.3 Patient population: (Specific inclusion and exclusion criteria are detailed in section 3)

### 1.1.4 Number of sites: 1, Boston Medical Center, [name]

### 1.1.5 Number of patients: 18 patients

### 1.1.6 Primary Objective:

- To determine the hematologic overall response rate (ORR) in IgM associated AL amyloidosis to a fixed dose of idelalisib. Response rates will categorized into complete response (CR), very good partial response (VGPR), partial response (PR) and progressive disease (PD) according to standard criteria (Gertz et al. 2010).

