### 1.1.7 Secondary Objectives:

- To assess progression free survival (defined as the interval from the first documentation of CR, VGPR or PR to the earlier of the first documentation of disease progression)
- To determine organ response (defined as improvement of involved organ function i.e. eGFR for kidneys, EF for heart etc.)
- To assess the safety and tolerability of idelalisib
- To measure impact on QOL of life using SF-36 assessment tool.

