## 3. PARTICIPANT SELECTION

### 3.1.1 Inclusion Criteria

Participants must meet the following criteria on screening examination to be eligible to participate in the study:

- 3.1.1** IgM paraprotein identified on serum immunofixation electrophoresis OR light chain-restricted CD20+ lymphoplasmacytic population on biopsy of bone marrow or lymph node (identified by H&E/immunohistochemistry or flow cytometry) OR positive myeloid differentiation primary response gene 88 (MYD88-L265P) OR *CXCR4WHIM* mutation on submitted samples
- 3.1.2** Biopsy-proven, relapsed or refractory AL amyloidosis
- 3.1.3** Age  $\geq$  18 years
- 3.1.4** ECOG performance status  $\leq$  2 (see Appendix A.)
- 3.1.5** Difference between serum free light chains (FLC) of  $>30$  mg/L or quantifiable IgM paraprotein  $>0.5$  g/L
- 3.1.6** Participants must have normal organ and marrow function as defined below:

- Absolute neutrophil count  $\geq 1,000/\text{mm}^3$
- Platelets  $\geq 50,000/\text{mm}^3$

**3.1.7** Ability to understand and the willingness to sign a written informed consent document.

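### VGPR is an absolute dFLC level below 40 mg/L, but patients may enter already below it, so unchanged disease can count as a primary-endpoint response

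*Combined protocol and SAP*

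**What the plan says.** The primary endpoint is the hematologic overall response rate (sections 1.1.6 and 12.1). Section 1.1.6 states: "Response rates will categorized into complete response (CR), very good partial response (VGPR), partial response (PR) and progressive disease (PD) according to standard criteria". Section 1.1.7 dates progression-free survival from "the interval from the first documentation of CR, VGPR or PR", which confirms that VGPR is a response category.

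Section 8.2 gives the amyloid criteria:

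- VGPR: "Difference in serum free light chains less than 40 mg/L".
- PR: a relative criterion, a reduction in dFLC of more than 50%.
- Stable disease: what is left over, "Meets neither criteria for CR, VGPR, PR or PD".
- PD for a patient not in CR begins "From VGPR, PR or SD, an increase in the serum M-protein from the lowest level by" more than 50%, with an absolute rise above 0.5 g/dL. The alternatives are a 50% rise in urine M-protein of more than 200 mg/day, or a light chain rise above 50% with an absolute magnitude above 100 mg/L.

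Inclusion item 3.1.5 requires "Difference between serum free light chains (FLC) of $>30$ mg/L or quantifiable IgM paraprotein $>0.5$ g/L".

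Section 8.1 limits response evaluability to "Only those participants who have measurable disease present at baseline, have received at least one cycle of therapy, and have had their disease re-evaluated", and adds: "These participants will have their response classified according to the definitions stated below". It does not define measurable disease. Section 12.4 puts every eligible enrolled patient in the main response analysis. Section 12.2 sets the rule: 9 patients, continue on at least 1 response, 9 more, success on at least 3 responses in total, with p0 = 0.05 and p1 = 0.25.

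**The concern.** The VGPR row looks at one value after treatment and never asks where the patient started. Two kinds of patient can meet it before the first dose:

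- those who qualify on dFLC with a value between 30 and 40 mg/L;
- those who qualify only on IgM, whose dFLC must be 30 mg/L or less, since otherwise they would qualify on dFLC.

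Because stable disease is residual, such a patient cannot be classed as stable while dFLC stays below 40 mg/L. Only PD can override the classification.

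The design treats each response as evidence of drug effect against a 5% background rate. A response that needs no change in disease breaks that link. With a threshold of 3 in 18, one or two such patients can decide the trial, and one in Stage 1 can remove the futility stop.

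The point concerns only patients who start below 40 mg/L. VGPR is sound for patients who start at 40 mg/L or more and cross the threshold.

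**Working it through.** **Step 1. Classify an unchanged patient under 8.2.** Take dFLC 35 mg/L at entry and at re-evaluation, with stable M-protein.

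- CR: not met if immunofixation is still positive.
- VGPR: 35 < 40, met.
- SD: excluded, because VGPR is met.
- PD: not met.

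The result is VGPR.

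PD leaves wide room. The serum M-protein limit is 0.5 g/dL = 5 g/L, and 5 / 0.5 = 10 times the IgM entry level. With dFLC steady at 35 mg/L and urine M-protein stable, IgM paraprotein rising from 1.0 to 5.9 g/L is an increase of 4.9 g/L = 0.49 g/dL. That is below the limit, and the patient is still VGPR.

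**Step 2. Reproduce the design.** Let X1 and X2 be the responses among the 9 patients of each stage.

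P(success) = Σ over x ≥ 1 of P(X1 = x) · P(X2 ≥ 3 − x).

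At p = 0.05:

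- P(X1 = 1) · P(X2 ≥ 2) = 0.2985 × 0.0712 = 0.0213
- P(X1 = 2) · P(X2 ≥ 1) = 0.0629 × 0.3698 = 0.0232
- P(X1 ≥ 3) = 0.0084
- Sum: 0.0529

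At p = 0.25 the same formula gives 0.835, against the stated 80% power. The chance of passing Stage 1 under p0 is 1 − 0.95^9 = 0.370. The type I error of 0.0529 is slightly above the stated 0.05, which is a separate matter. It serves here as the reference value.

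**Step 3. Add fixed numbers of low-dFLC patients.** All other patients respond at 5%. Suppose first that each low-dFLC patient stays below 40 mg/L without PD (s = 1, the upper bound).

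- One, in Stage 1: Stage 1 is passed with certainty, and 2 or more of the other 17 are needed: 1 − 0.95^17 − 17 × 0.05 × 0.95^16 = 0.208.
- One, in Stage 2: 0.2985 × (1 − 0.95^8) + 0.0712 = 0.172.
- Two, at least one in Stage 1: 1 − 0.95^16 = 0.560.
- Two, both in Stage 2: only Stage 1 has to be passed, 0.370.
- Three, at least one in Stage 1: 1.000. All three in Stage 2: 0.370.

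If each has only a 50% chance of staying below 40 mg/L (s = 0.5), each counts as a responder with probability 0.5 + 0.5 × 0.05 = 0.525. One patient then gives 0.112 to 0.130, two give 0.192 to 0.257, and three give 0.256 to 0.420.

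**Step 4. Add a random share q.** The response probability per patient becomes p = q·[s + (1 − s)·0.05] + (1 − q)·0.05. The shares are assumptions.

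| q | p (s = 1) | Pass Stage 1 (s = 1) | Success (s = 1) | p (s = 0.5) | Success (s = 0.5) |
|---|---|---|---|---|---|
| 0 | 0.05 | 0.370 | 0.053 | 0.05 | 0.053 |
| 5% | 0.0975 | 0.603 | 0.234 | 0.07375 | 0.131 |
| 10% | 0.145 | 0.756 | 0.464 | 0.0975 | 0.234 |
| 20% | 0.24 | 0.915 | 0.812 | 0.145 | 0.464 |

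If the drug produces no response in anyone (p = q, s = 1), success still has probability 0.246 at a 10% share and 0.694 at 20%.

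**Step 5. Test the fix.** Low-dFLC patients now count only on CR or a more than 50% dFLC reduction. Under the null, the false-success probability is 0.053 if they respond at 5% like the others. If they cannot respond, p = (1 − q) × 0.05 gives 0.047, 0.041 and 0.030 at the three shares.

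**The case against.** The best counter-argument rests on 8.1. It says that only patients with measurable disease are evaluable and have their response classified, while 12.4 says only who is in the analysis. Read together, a patient too low on dFLC to be measured could stay in the denominator unclassified, and the gap would be one missing definition. That reading is possible, but the text does not state it. The nearest thing the protocol has to a definition of measurable disease is item 3.1.5 itself, which admits these patients.

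Sections 1.1.2 and 1.1.6 also refer to a cited consensus paper that may carry a baseline condition. That cannot be checked here. Section 8.1 classifies patients by the definitions printed in the protocol, and those contain no such condition.

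The size is fairly challenged. The share of low-dFLC patients is not documented, the 30 to 40 mg/L window is narrow, and the largest figures assume that every such patient stays below 40 mg/L. This stands: the figures are scenarios, not an estimated error rate.

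The Waldenström criteria in 8.3 would show most unchanged patients as stable, but that report is additional and does not govern Stage 1 or the success rule. The PD example in step 1 only shows how rarely PD would override VGPR. The fix does not alter the PD limits.

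Finally, the fix leaves open a more than 50% fall from a very low baseline, which may be only a few mg/L. If that happened by chance in 20% or 30% of low-dFLC patients (assumed), at a 20% share p is 0.08 or 0.10 and false success is 15.6% or 24.6%. This also stands. It is a PR route already in 8.2, and it remains far below the 81% at that share under the current text.

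**Conclusion.** The concern holds. Followed as written, sections 8.2, 3.1.5 and 12.4 together score unchanged disease as a primary-endpoint response for any patient who enters and stays below 40 mg/L without progression. This is an error in the stated rule, and it does not depend on how many such patients enrol.

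Its effect does depend on that number. One such patient raises the false-success probability from 5.3% to 17% to 21% if dFLC stays below 40 mg/L, and to 11% to 13% if there is only an even chance of that. One in Stage 1 who stays below 40 mg/L makes continuation certain, against 37% under the null. Three who stay below it, at least one in Stage 1, satisfy the success rule with no other response. These figures assume the 9 + 9 rule, independent patients, and a 5% response rate in everyone else. The point should be settled before any response is classified for the Stage 1 decision.

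**What to change.** State in 8.2 and 12.4 that patients with baseline dFLC below 40 mg/L stay in the denominator but cannot be VGPR on the absolute level alone. For the primary response rate they count only if they meet CR or the more than 50% dFLC reduction. Leave VGPR unchanged for patients with baseline dFLC of 40 mg/L or more. Align the term measurable disease in 8.1 with this rule. Report the IgM-based response of the low-dFLC patients under 8.3 as secondary, and list their baseline and follow-up dFLC so that a PR resting on a fall of a few mg/L can be seen.

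Costs:

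- **Conduct.** No new test, since the free light chain assay is already scheduled at enrollment and follow-up visits (section 7.0). A protocol amendment is needed, with manufacturer review and IRB approval (section 11.1).
- **Reported response rate.** With s = 1 the drop is q × (1 − p). At shares of 5%, 10% and 20% that is at most 4.8, 9.5 and 19.0 points if the true rate is 5%, and 3.8, 7.5 and 15.0 points if it is 25%. If low-dFLC patients cannot respond at all under the new rule, it is at most 5, 10 and 20 points.
- **Power.** It stays at 0.835 if low-dFLC patients respond at 25% like the others. At half that rate it is 0.821, 0.805 and 0.772 at the three shares. If they cannot respond it is 0.805, 0.772 and 0.694, so it falls below the planned 80% at shares of 10% and 20%.

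A minimum baseline dFLC for dFLC-based response, or a separate prespecified criterion for low-dFLC patients, would also close the gap. The rule above changes the least.

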## OBJECTIVES

### 1.1.1 Title: Idelalisib for IgM-Associated AL Amyloidosis

### 1.1.2 Study Design:

This is a single arm, open label study designed to evaluate the safety and efficacy of idelalisib in patients with relapsed IgM-associated AL amyloidosis. Treatment will be comprised of idelalisib at 100mg orally twice daily, with permitted dose modifications for toxicity per manufacturer guidelines (Section 5). The medication will be continued until progression or significant toxicity.

After giving written informed consent, subjects will be evaluated for eligibility for enrollment in the study. Baseline evaluations will be performed as outlined in Section 7. Subjects who satisfy all inclusion and exclusion criteria will begin the study drug. Subjects will be monitored every cycle for safety and hematologic status. Organ function will also be measured during therapy.

Participants will be eligible to continue therapy as long as they do not demonstrate progressive disease or unacceptable toxicity. Standard response criteria for AL amyloidosis hematologic and organ response will be used (Gertz et al. 2010). Hematologic response will also be categorized and reported by Waldenstrom's macroglobulinemia hematologic response criteria. For the purposes of defining progressive disease, the amyloid response criteria will be used. Overall response rate will be measured and participants will be categorized into complete response, very good partial response, partial response and progressive disease. Progression free survival, organ response, safety and tolerability of idelalisib, and quality of life will be assessed.

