### 8.3 Waldenstrom's Macroglobulinemia Hematologic Response Criteria

CATEGORY	RESPONSE CRITERIA
Complete response (CR)	
 
Serum IgM values in normal range
 
Disappearance of monoclonal protein by immunofixation
 

Very good partial response (VGPR)	
 
Monoclonal IgM protein is detectable
 
At least 90% reduction of serum IgM from baseline or serum IgM values in normal range
 

Partial Response (PR)	
 
Monoclonal IgM protein is detectable
 
At least 50% but <90% reduction of serum IgM from baseline
 

Minor Response (MR)	
 
Monoclonal IgM protein is detectable
 
At least 25% but <50% reduction of serum IgM from baseline
 

Stable disease (SD)	
 
Monoclonal IgM protein is detectable
 
<25% reduction and <25% increase in serum IgM from baseline
 

Progressive disease (PD)	
 
≥25% increase in serum IgM with a total increase of at least 500 mg/dL from nadir 
 
Reconfirmation of initial IgM increase is required when IgM is sole criterion for PD confirmation.
 
 
 

1. Nadir is defined as the lowest serum IgM value obtained at any time from baseline onwards with the exception that serum IgM levels post-plasmapheresis will not be considered for up to 6 weeks.

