#### 8.5 Progression-Free Survival

Progression-Free Survival (PFS) is defined as the duration of time from start of treatment to time of objective disease progression (including initiation of new therapy or death). Follow-up will continue until disease progression, which we anticipate to be no more than 2 years.

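### Progression under section 8.2 can rest on one unconfirmed laboratory value above the patient's lowest level, so PFS can be biased short in patients with persistently high values

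*Combined protocol and SAP*

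**What the plan says.** **Which criteria decide progression.** Section 1.1.2: "For the purposes of defining progressive disease, the amyloid response criteria will be used". Section 8.2 therefore governs and section 8.3 does not.

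**The governing rule (8.2, progressive disease row).** For a patient in VGPR, PR or SD there are three routes.
- Serum M-protein: "From VGPR, PR or SD, an increase in the serum M-protein from the lowest level by" more than 50%, "as long as the absolute magnitude of this increase is" above 0.5 g/dL.
- Urine M-protein: a 50% rise from the lowest level, with the increase above 200 mg/day.
- Light chain: "an increase in the serum or urine monoclonal free light chain by" more than 50% from the lowest level, with an absolute magnitude above 100 mg/L. This clause does not say whether the 100 mg/L is the increase or the level reached.

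For a patient in CR the M-protein rule uses fixed levels instead ("From CR, an increase in serum M-protein to" above 0.5 g/dL, or urine above 200 mg/day), and the light-chain rule is an increase above 100 mg/L. No route mentions a repeat value.

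**The non-governing rule (8.3).** "Reconfirmation of initial IgM increase is required when IgM is sole criterion for PD confirmation". IgM is the only progression criterion that row lists.

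**The endpoint.** Section 8.5 defines PFS as the "duration of time from start of treatment to time of objective disease progression (including initiation of new therapy or death"). Section 1.1.7 starts the clock at first response and ends it at the first recorded progression. Neither requires confirmation. Nor do sections 4.1.3, 4.1.4, 7.0 or 12.

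**The concern.** The only safeguard against progression on a single value sits in the criteria set that does not decide progression. Under 8.2 the comparison is with the lowest value so far. As visits accumulate, that minimum can only stay the same or fall, while each new visit is another chance of a high reading. A patient whose disease has not changed can therefore cross the line through assay and biological variation.

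At stake is the PFS estimate, a named secondary endpoint in a single arm of at most 18 patients. False events shorten PFS, there is no control arm to share the bias, and no text withdraws a progression date once it is recorded.

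**Working it through.** The documents give no false-progression rate or PFS target to reproduce, so the check is whether the written thresholds already make the problem negligible.

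**Inputs from the protocol**
- Thresholds: section 8.2, as above.
- Visits: section 4.1.4, monthly for three months and then every three months. With baseline this gives values at months 0, 1, 2, 3, 6, 9, 12, 15, 18, 21 and 24, that is 11 values.
- Horizon: 24 months, the expected maximum in section 8.5.

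**Assumptions not in the documents**
- A constant true level with independent log-normal noise.
- Within-patient CV of 10%, 15% or 20%.
- The true levels themselves.

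**Step 1: where the absolute threshold protects.** For the increase reading, the two conditions coincide at a lowest level of 100 / 0.5 = 200 mg/L for light chains and 0.5 / 0.5 = 1 g/dL for serum M-protein. Below those points the absolute condition is the stricter one and protects the patient. Above them only the 50% rule matters.

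**Step 2: hand check of the 50% rule.** With σ = √ln(1 + CV²), the chance that one given later value exceeds 1.5 times one given earlier value is 1 − Φ(ln 1.5 / (σ√2)).

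| CV | σ | ln 1.5 / (σ√2) | Chance per pair | × 55 pairs |
|---|---|---|---|---|
| 10% | 0.0998 | 0.4055 / 0.1411 = 2.874 | 0.0020 | 0.11 |
| 15% | 0.1492 | 0.4055 / 0.2110 = 1.922 | 0.0273 | 1.50 |
| 20% | 0.1980 | 0.4055 / 0.2801 = 1.448 | 0.0739 | 4.06 |

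Eleven values give 11 × 10 / 2 = 55 such pairs. The last column is an expected count and bounds the probability from above. At a CV of 10% false progression cannot exceed about 11%. At 15% and 20% the bound gives no protection.

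**Step 3: simulation.** There were 200,000 stable patients per setting. Each value was tested against the minimum of all earlier values with both thresholds applied. The repeat is one independent value that must meet the rule against the same lowest level. The table shows false progression by month 24, without → with one repeat.

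| True level (100 mg/L read as the increase) | CV 10% | CV 15% | CV 20% |
|---|---|---|---|
| Light chain 100 mg/L | 0 → 0% | 0 → 0% | 2 → 0% |
| Light chain 150 mg/L | 0 → 0% | 4 → 0.1% | 26 → 2% |
| Light chain 200 mg/L | 1 → 0% | 26 → 2% | 62 → 14% |
| Light chain 300 mg/L | 8 → 0.7% | 54 → 16% | 84 → 45% |
| Serum M-protein 0.5 g/dL | 0 → 0% | 0 → 0% | 2 → 0% |
| Serum M-protein 1 g/dL | 1 → 0% | 26 → 2% | 62 → 14% |

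At 60 mg/L the figure is 0% in every column. The 300 mg/L row at a CV of 10% (8%) agrees with the bound in step 2.

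**Step 4: the other reading.** If 100 mg/L is the level reached, the absolute condition stops protecting near 100 mg/L. False progression at true levels of 100 mg/L and above is then about 8%, 54% and 84% without a repeat. The choice of reading moves the 100 mg/L row from at most 2% to as much as about 83%.

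Urine M-protein was not simulated.

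**The case against.** The strongest reply is that 8.2 already has two guards, a 50% rise and an absolute threshold, and that patients can enter at levels where these suffice. Section 3.1.1 requires only a light-chain difference above 30 mg/L or an IgM paraprotein above 0.5 g/L (0.05 g/dL). On the increase reading the simulated risk at such levels is essentially nil. The documents give neither the distribution of levels nor the CV. All of this stands, and it means the plan's PFS bias has no known size.

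Several stronger readings are tempting but not supported.
- *Any value above the minimum is progression.* It is not: both thresholds must be met, and from CR the M-protein rule uses no running minimum.
- *Sections 8.2 and 8.3 contradict each other.* They are different criteria with different thresholds (more than 50% against 25%), and confirming a smaller rise does not oblige one to confirm a larger one. The gap is an unprotected rule.
- *Progression always ends follow-up.* Section 4.1.4 reads that way, but sections 4.1.3 and 5.1.1 let a patient who meets progression continue at the Principal Investigator's discretion, and calendar footnote 6 runs visits while on drug or until progression. Loss of later data is possible, not certain.
- *The trial's success decision is at risk.* Section 12.2 decides on at least 3 responses, which this does not touch. Section 12 gives no test or target for PFS.

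It is also fair to say that a repeat leaves the running minimum in place and does not remove all false events.

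**Conclusion.** The point holds in a limited form. Section 8.2 lets one unconfirmed value count as progression, section 8.5 makes that a PFS event, and the protocol's only reconfirmation rule lies outside the governing criteria. Where values stay high (light chain about 200 mg/L or more, or serum M-protein about 1 g/dL or more) and the CV is 15% or more, a stable patient's chance of a false event over two years runs from about a quarter to over four fifths. One repeat cuts this substantially. With a CV of 10% it is 8% or less. At 100 mg/L or below it is at most 2% for CVs up to 20%, but only if the 100 mg/L condition means the increase.

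These figures are illustrations that rest on the assumed CV, level and independent noise. They do not estimate the bias in this trial. The effect is confined to a secondary, untested endpoint, so this is a cheap improvement and not a flaw in the primary analysis.

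**What to change.** For the PFS endpoint, state the following in sections 8.2 and 8.5.
1. Progression based only on serum M-protein, urine M-protein or light chain counts when a repeat sample (the next scheduled one or an earlier one) also meets the criterion against the same lowest level. The event is dated at the first rise.
2. If no repeat is obtained, or if death or new therapy comes first, the event counts as section 8.5 already provides.
3. The 100 mg/L light-chain condition means either the increase or the level, and the text says which.
4. PFS on unconfirmed progression is reported as a sensitivity analysis.

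When 8.5 is edited, its starting point should be reconciled with section 1.1.7. The text on continuing treatment and visits (sections 4.1.3, 4.1.4 and 5.1.1) should be reconciled with the endpoint rule by the protocol team; this point proposes no treatment rule.

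**Cost.** A few sentences, a short delay before an event is confirmed, and a repeat test at each unconfirmed rise. That can be more than one per patient: at 300 mg/L and a CV of 20% the simulation gives about 1.46 per patient, or 1.46 × 18 ≈ 26 in all. Some false progression remains (45% in that same extreme setting, against 84% without a repeat).
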